5.4. Concomitant Medications / Treatments

Necessary supportive measures for optimal medical care may be given throughout the study, including IV antibiotics to treat infections, blood components, and antiemetics. Additional care will be administered as indicated by the treating physician and the patient's medical need. No concomitant cytotoxic therapy, whether conventional or investigational, will be allowed during this study. All concomitant medications and supportive therapy must be recorded on the appropriate CRF.

The use of grapefruit or grapefruit juice and St. John's Wort (hyperforin) is prohibited during study treatment. The treating investigator is to discuss this with the patient prior to initiating study treatment and will review list of all medications and supplements during the course of the study.

Medications with a known risk of TdP are prohibited during the course of the study. Refer to Appendix F1. Use caution with medications with a possible risk of TdP or a conditional risk of TdP. Refer to Appendix F2 and F3.

Radiotherapy may be allowed while the patient is enrolled in this study if given to help palliate a specific symptom (e.g. bone pain, brain metastases, etc.).

5.5. Concomitant Therapies Requiring Caution

5.5.1. Vemurafenib

- **Strong CYP3A4 inhibitors:** Coadministration of a strong CYP3A4 inhibitor increased vemurafenib plasma concentration and may lead to increased toxicity. Avoid coadministration of vemurafenib with strong CYP3A4 inhibitors, if this is unavoidable consider dose reduction of vemurafenib, if clinically indicated. Refer to Appendix G, Table 1 for a compiled list of CYP3A4 inhibitors.
- **Strong CYP3A4 inducers:** Coadministration of vemurafenib with rifampin, a strong CYP3A4 inducer, decreased vemurafenib plasma concentration and may result in decrease efficacy. Avoid coadministration of vemurafenib with strong CYP3A4 inducers (e.g. phenytoin, carbamazepine, rifampin for the duration of the study. Refer to Appendix G, Table 2 for a compiled list of CYP3A4 inducers.
- **CYP1A2 Substrates:** Coadministration of vemurafenib with tizanidine, a sensitive CYP1A2 substrate, increased tizanidine systemic exposure by 4.7-fold. Avoid concomitant use of vemurafenib with drugs having a narrow therapeutic window that are primarily metabolized by CYP1A2. If coadministration cannot be avoided, monitor closely for toxicities, and consider a dose reduction of concomitant CYP1A2 substrates. Refer to Appendix H for a compiled list of CYP1A2 major substrates.
- **P-gp Substrates:** Coadministration of vemurafenib with digoxin, a sensitive P-glycoprotein (P-gp) substrate, increased digoxin systemic exposure by 1.8-fold. Avoid concurrent use of P-gp substrates known to have narrow therapeutic indices. If use of these medications is unavoidable, consider dose reduction of P-gp substrate.
- **Warfarin:** INR (International Normalization Ratio) monitoring should be considered when Vemurafenib is used concurrently with warfarin.

5.5.2. Sorafenib

- **Strong CYP3A4 inhibitors:** Ketoconazole, a strong inhibitor of CYP3A4 and P-glycoprotein, administered at a dose of 400mg once daily for 7 days did not alter the mean AUC of a single oral dose of sorafenib 50mg in healthy volunteers. Refer to Appendix G, Table 1 for a compiled list of CYP3A4 inhibitors.
- **Strong CYP3A4 inducers:** Rifampin, a strong CYP3A4 inducer, administered at a dose of 600mg once daily for 5 days with a single oral dose of sorafenib 400mg in healthy volunteers resulted in a 37% decrease in the mean AUC of

sorafenib. Avoid concomitant use of strong CYP3A4 inducers (such as carbamazepine, dexamethasone, phenobarbital, phenytoin, rifampin, rifabutin, St. John's wort), when possible because these drugs can decrease the systemic exposure to sorafenib. Refer to Appendix G, Table 2 for a compiled list of CYP3A4 inducers.

- **Neomycin:** Neomycin administered as an oral dose of 1g three times daily for 5 days decreased the mean AUC of sorafenib by 54% in healthy volunteers administered a single oral dose of sorafenib 400mg. The effects of other antibiotics on the pharmacokinetics of sorafenib have not been studied.
- **Drugs that increase Gastric pH:** The aqueous solubility of sorafenib is pH dependent, with higher pH resulting in lower solubility. However, omeprazole, a proton pump inhibitor, administered at a dose of 40mg once daily for 5 days did not result in a clinically meaningful change in sorafenib single dose exposure. No dose adjustment of sorafenib is considered necessary.
- **Effect of sorafenib on other drugs:** Sorafenib 400mg twice daily for 28 days did not increase the systemic exposure of concomitantly administered midazolam (CYP3A4 substrate), dextromethorphan (CYP2D6 substrate), and omeprazole (CYP2C19 substrate).

5.6. Duration of Therapy

In the absence of treatment delays due to adverse events, treatment may continue until:

- Disease progression
- Inter-current illness that prevents further administration of treatment
- Unacceptable adverse event(s)
- Patient decides to withdraw from the study, OR
- General or specific changes in the patient's condition render the subject unacceptable for further treatment in the judgment of the investigator

5.7. Duration of Follow-up

Patients will be followed for adverse events for 30 days following the last dose of study treatment. Patients will be followed for survival status every 3 months until study completion (this may be completed through medical record review or follow up phone calls).

5.8. Removal of Subjects from Protocol Therapy

Patients will be removed from study treatment when any of the criteria listed in Section 5.6 apply. The reason for study removal and the date the patient was removed will be documented in the Case Report Form. The patient should complete the end of treatment visit and followed-up per protocol (Sections 6.5, 6.5).

5.9. Subject Replacement

Patients who receive any number of doses of both agents (Vemurafenib + Sorafenib) and has a scan after at least 2 cycles of treatment will not be replaced. Therefore, any

patient that does not meet this criteria will be replaced in order to achieve 7 evaluable patients.

6. STUDY PROCEDURES

6.1. Screening / Baseline Procedures

Assessments performed exclusively to determine eligibility for this study will be done only after obtaining informed consent. Assessments performed for clinical indications (not exclusively to determine study eligibility) may be used for baseline values even if the studies were done before informed consent was obtained.

All screening procedures must be performed within 28 days prior to initiated study treatment unless otherwise stated. The screening procedures include:

- Informed Consent
- Medical History -To include concurrent baseline conditions (using NCI CTCAE, version 5.0), prior cancer therapy (including documentation of prior surgery, adjuvant or neoadjuvant chemotherapy and radiotherapy).
- ECOG Performance Status (Appendix B)
- Review inclusion / exclusion criteria
- Vital Signs (blood pressure, pulse, respiratory rate, and temperature)
- Complete physical examination including height (cm) and weight (kg)
- Concomitant medication notation to include all medications taken in the last 30 days
- Hematology: CBC with differential and platelet count
- Serum chemistries: glucose, creatinine, BUN, total bilirubin, AST, ALT, alkaline phosphatase, albumin, LDH, total protein, and electrolytes (sodium, potassium, chloride, CO₂, magnesium, calcium). In patients with known Gilbert's syndrome, it is recommended to perform a direct bilirubin and indirect bilirubin. Calculate creatinine clearance (the Cockcroft-Gault equation may be used to calculate the creatinine clearance at any of the time points in this protocol)
- Coagulation: PT, INR
- CA19-9 (or CA 125, or CEA if not expressers of CA 19-9)
- Serum pregnancy test for WOCBP within 72 hours prior to the first dose of study treatment.
- Electrocardiogram (ECG)
- Computed tomography (CT) / magnetic resonance imaging (MRI) scan to document disease status (including chest, abdomen, pelvis, and other regions as clinically indicated. In addition, brain scan is required to exclude brain metastases if clinically indicated only. If a CT scan was taken within 28 days prior to first dose, a new scan is not necessary. (RECIST 1.1 criteria Section 7.1)
- Blood for correlative analysis - 3 X 10 mL

- Confirm KRAS and BRAF mutation status by tissue biopsy. For those patients in which the mutation status of KRAS and BRAF kinases has not previously been determined, the patient must have an archival tumor specimen (primary or metastatic site) available to submit to confirm KRAS and BRAF status. The results of the mutation status are required for determining patient's eligibility for this trial.

6.2. Optional Tissue Collection

As part of participation in this trial, subjects will be provided the option to consent to the collection of tumor tissue for Reverse Phase Protein Array (RPPA) analysis.

For those patients that consent to the optional tissue collection for RPPA analysis, tissue will be collected from a newly obtained core or excisional biopsy of a tumor lesion if performed recently (within 30 days prior to study treatment on Day 1) and during their participation in the study should they be scheduled for a biopsy as part of their routine care through the follow-up period.

Tissue samples will be centrally analyzed by Theralink. Details for processing and shipping of the tissue will be provided in the Trial Lab Manual.

6.3. Procedures During Treatment (Cycle is 28 Days)

Patients must begin Cycle 1 within 28 days of signing the informed consent document and after the screening assessments. All assessments should be performed within 72 hours of each specified time parameter, with the exception of Cycle 1 in which assessments must be conducted within 24 hours (except those noted), or if medical or scheduling conditions require a delay.

6.3.1. Day 1 of Each Cycle

- Inclusion/exclusion review (Cycle 1 only)
- Directed Physical exam
- Vital Signs (blood pressure, pulse, respiratory rate, and temperature)
- Measurement of weight (kg) and BSA calculation prior to dosing
- ECOG Performance Status
- Hematology: CBC with differential and platelet count
- Serum chemistries: glucose, creatinine, BUN, total bilirubin, AST, ALT, alkaline phosphatase albumin, LDH, total protein, and electrolytes (sodium, potassium, phosphorus, chloride, CO₂, magnesium, calcium). In patients with known Gilbert's syndrome, it is recommended to perform a direct bilirubin and indirect bilirubin. Calculate creatinine clearance (Cockcroft-Gault equation)
- Coagulation: PT, INR – only required for patients on warfarin
- Serum Pregnancy Test
- ECG (Cycles 1 through 3, then every 3 cycles 6, 9, 12 etc.)
- Blood for correlative analysis- 3 X 10 mL (cycle 2 and beyond)
- AEs using the NCI CTCAE 5.0

- Concomitant medication notation
- Distribute study medications to the patient and provide the Patient Study Drug Diary (Appendix E) and provide instructions to the patient to return on day 1 of each cycle.
- Cycle 2 and beyond: Complete Drug Accountability (Per Section 9.4): Collect previous cycle study medications and review the completed Patient Study Drug Diary with the patient and address any discrepancies with the patient.

6.3.2. Days 8, 15 and 22 of Cycle 1

- Directed physical exam
- Vital Signs (blood pressure, pulse, respiratory rate, and temperature)
- ECOG Performance Status
- Hematology: CBC with differential and platelet count
- Serum chemistries: glucose, creatinine, BUN, total bilirubin, AST, ALT, alkaline phosphatase albumin, LDH, total protein, and electrolytes (sodium, potassium, phosphorus, chloride, CO₂, magnesium, calcium). In patients with known Gilbert's syndrome, it is recommended to perform a direct bilirubin and indirect bilirubin. Calculate creatinine clearance (Cockcroft-Gault equation)
- ECG (Cycle 1/ Day 15 only)
- AEs using the NCI CTCAE 5.0
- Concomitant medication notation

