3.2. Secondary Objectives

- To confirm the safety of giving Vemurafenib + Sorafenib to patients with advanced pancreatic cancer.
- To determine the clinical activity of Vemurafenib + Sorafenib as defined Progression free survival (PFS) and Overall survival (OS) rate.
- To utilize circulating tumor DNA (ct DNA) in plasma to give qualitative (mutations) and to some extent quantitative (amount of ct DNA) information

regarding BRAF and KRAS. This will be measured at baseline and just before each cycle

- To measure phospho ERK and phospho AKT in plasma samples to determine if the treatment has hit the intended target (Takano et al. 2010, Petricoin 2009). This will be measured at baseline and just before each cycle.

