4.2. Exclusion Criteria

- 1. Is currently participating and receiving trial therapy or has participated in a trial of an investigational agent and received trial therapy or used an investigational device within 2 weeks of the first dose of this trials' treatment.
- 2. Has had prior chemotherapy, targeted small molecule therapy, or radiation therapy within 2 weeks prior to Cycle 1/Day 1 or who has not recovered (i.e. NCI-CTC AE Version 5.0 \leq Grade 1 at the time of signing informed consent) from adverse events due to a previously administered agent(s).

Note: Patients with \leq Grade 2 neuropathy and \leq Grade 2 alopecia are an exception to this criterion and may qualify for the trial.

- 3. Previous BRAF inhibitor use such as vemurafenib, GSK2118436 or sorafenib.
- 4. If patient received major surgery, and has not yet recovered adequately from the toxicity and/or complications from the intervention prior to starting therapy.
- 5. Previously untreated or concurrent cancer that is distinct in primary site or histology from pancreatic cancer except cervical cancer in-situ, treated basal cell carcinoma, or superficial bladder tumor. Subjects surviving a cancer that was curatively treated and without evidence of disease for more than 3 years before

study entry. All cancer treatments must be completed at least 3 years prior to study entry (i.e., signature date of the informed consent form).

6. Has known active central nervous system (CNS) metastases and/or carcinomatous meningitis. Patients with previously treated brain metastases may participate provided they are stable (without evidence of progression by imaging for at least four weeks prior to the first dose of trial treatment and any neurologic symptoms have returned to baseline), have no evidence of new or enlarging brain metastases, and are not using steroids for at least 7 days prior to trial treatment. This exception does not include carcinomatous meningitis, which is excluded regardless of clinical stability.
7. Uncontrolled hypertension (systolic pressure >140 mm Hg or diastolic pressure > 90 mm Hg [NCI-CTCAE v5.0] on repeated measurement) despite optimal medical management.
8. Active of clinically significant cardiac disease including:
 - a. Congestive heart failure New York Heart Association (NYHA) > Class II. (Appendix D)
 - b. Active coronary artery disease (CAD)
 - c. Cardiac arrhythmias requiring anti-arrhythmic therapy other than beta blockers or digoxin.

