10. CORRELATIVES / SPECIAL STUDIES

10.1. Trial Specimens

Blood specimens will be collected for plasma DNA to determine target engagement before, during and after treatment. This will be measured at baseline and just before each cycle of treatment. The site will collect blood samples (3 X 10 mL) at screening, Day 1 of each treatment cycle, and at the off treatment study visit.

Please see Laboratory Manual for details on blood collection and processing guidelines.

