10.2. Assay Methodology

Blood samples will be collected and processed for plasma at baseline and just before each treatment cycle. Plasma will be used to analyze circulating tumor DNA (ctDNA) to give qualitative (mutations) and to some extent quantitative (amount of ctDNA) information regarding BRAF and KRAS.

Blood samples will be collected and processed for serum at baseline and just before each treatment cycle. Serum will be analyzed using the Bio-plex suspension array using specific antibodies and flow cytometry as per the methods developed by Takano et al. 2010 to measure phospho ERK to determine if the treatment has hit the intended target.

Tissue samples

For those patients that consent to the optional tissue collection for RPPA analysis, tissue will be collected from a newly obtained core or excisional biopsy of a tumor lesion if performed recently (within 30 days prior to study treatment on Day 1) and during their participation in the study should they be scheduled for a biopsy as part of their routine care during their participation in the study through the follow-up period.

Tissue samples will be analyzed using Reverse Phase Protein Array (RPPA).

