11.3.4. Statistical Analysis

The primary efficacy analysis will focus on the disease control rate (CR + PR + SD at 16 weeks). Secondary endpoints include progression-free survival (PFS) and overall survival (OS). The efficacy analysis will only be conducted on patients who have received any number of doses of both agents (vemurafenib + sorafenib) and have a scan after at least 2 cycles of treatment.

Objective responses will be evaluated using the Response Evaluation Criteria In Solid Tumors 1.1 (RECIST 1.1). Changes (i.e. improvements) in tumor measurements from baseline values will be assigned a status of CR or PR or SD. Objective response measurements will comprise the sum of CR plus PR. The overall response rate, as well as the rates for the individual categories of response (i.e. CR, PR, SD, and PD), will be estimated by the percentage of patients achieving these criteria with exact 95% binomial confidence intervals.

Progression-free survival is defined as the interval from the date of study treatment initiation (C1/D1) to the earliest date of documented evidence of recurrent or progressive disease, or the date of death due to any cause, whichever occurs first. Overall survival will be measured from the date of study treatment initiation (C1/D1) to the date of death

due to any cause, or the date of last contact (censored observations). For the estimation of progression-free and overall survival a Kaplan-Meier analysis will be performed.

Longitudinal measurements of circulating tumor DNA (ctDNA) and phospho ERK will be visualized using plots for each evaluable patient. These measurements will be transformed using a logarithmic transformation, if necessary, to remove skewness. Significant changes across time will be assessed using linear mixed effects models, to account for the correlation among the measurements within an individual. If the observed change is non-linear, nonlinear mixed effects models will be used.

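### The visit schedule omits the Cycle 1 Day 1 correlative blood sample that Section 10.1 requires, and phospho-AKT in blood has no assay or analysis

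*Combined protocol and SAP*

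**What the plan says.** **Sampling times.** Section 10.1 collects blood "at screening, Day 1 of each treatment cycle, and at the off treatment study visit". The secondary objectives (Section 3.2) and Section 10.2 speak of baseline and just before each cycle. The operational text differs. Section 6.1 lists "Blood for correlative analysis - 3 X 10 mL" at screening, Section 6.3.1 has "Blood for correlative analysis- 3 X 10 mL (cycle 2 and beyond", and Appendix A marks screening, Day 1 from Cycle 2 onward and the off-treatment visit, leaving C1D1 blank.

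**Windows.** Section 6.1: "All screening procedures must be performed within 28 days prior to initiated study treatment unless otherwise stated". No tighter limit is set for the correlative tubes. Exclusion 2 in Section 4.2 bars a patient who "Has had prior chemotherapy, targeted small molecule therapy, or radiation therapy within 2 weeks prior to Cycle 1/Day 1".

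**Analytes and matrix.** Section 3.2 has the objective "To measure phospho ERK and phospho AKT in plasma samples to determine if the treatment has hit the intended target", and the synopsis and Section 3.4.2 list both phosphoproteins among the secondary endpoints. In Section 10.2, "Serum will be analyzed using the Bio-plex suspension array using specific antibodies", and the only phosphoprotein named for that assay is phospho-ERK. Section 11.3.4 says "Longitudinal measurements of circulating tumor DNA (ctDNA) and phospho ERK will be visualized using plots for each evaluable patient", followed by mixed-effects models of change over time. Phospho-AKT does not appear there.

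**The concern.** These samples are meant to show whether the drugs reached their target, so the analysis needs a reference value taken close to the first dose. The trial has one arm, and no control group can show how the markers would have moved without treatment. If the reference is the screening draw, the change to C2D1 combines the study-drug effect with whatever happened between screening and first dose. That may include untreated growth and, for some patients, the tail of a previous regimen. A sample missed before the first dose cannot be recovered later.

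For phospho-AKT the problem is simpler. A team that follows Sections 10.2 and 11.3.4 as written would produce no blood phospho-AKT data for a declared secondary endpoint.

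**Working it through.** The plan states no figure for this point, so there is none to reproduce. The check is a comparison of sections, a day count and one labelled illustration.

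**Sampling times side by side**

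| Source | Screening | C1D1 | Day 1, Cycle 2 on | Off treatment |
|---|---|---|---|---|
| Section 10.1 | yes | yes | yes | yes |
| Sections 6.1, 6.3.1 and 6.4 | yes | no | yes | yes |
| Appendix A | yes | blank | yes | yes |

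**Day count.** Inputs: screening window 28 days (Section 6.1), washout 14 days before C1D1 (exclusion 2), cycle length 28 days (Section 5.1), Cycle 1 assessment tolerance 24 hours (Section 6.3).

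- Days on which the screening draw may be taken while prior therapy is still permitted: 28 − 14 = 14 (days −28 to −15), and 14/28 = 50% of the window.
- Nominal interval from screening baseline to C2D1: from 28 + 0 = 28 to 28 + 28 = 56 days, before the 72-hour visit tolerance.
- Largest share of that interval before any study drug: 28/56 = 50%.
- With a pre-dose C1D1 sample: baseline age at most 1 day, interval 28 to 29 days, and no overlap with permitted prior therapy.

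**Illustration of drift.** The documents give no ctDNA growth rate. Assume untreated ctDNA doubles every d weeks, with d from 4 to 8. A baseline that is a weeks old understates the pre-dose level by the factor 2^(a/d). A true halving from C1D1 to C2D1 then appears as the ratio 0.5 × 2^(a/d).

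| Baseline age | d | Drift factor | Apparent ratio after a true halving |
|---|---|---|---|
| 28 days | 4 weeks | 2.00 | 1.00 |
| 28 days | 6 weeks | 1.59 | 0.79 |
| 28 days | 8 weeks | 1.41 | 0.71 |
| 14 days | 6 weeks | 1.26 | 0.63 |
| 7 days | 6 weeks | 1.12 | 0.56 |

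The 28-day rows are the worst case the window allows. Growth alone would hide a fall rather than create one. If the draw coincides with prior chemotherapy, the direction of the bias is unknown. No comparable figure can be given for phospho-ERK.

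**Phosphoproteins in blood side by side**

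| Source | phospho-ERK | phospho-AKT | Matrix |
|---|---|---|---|
| Objective, Section 3.2 | yes | yes | plasma |
| Assay, Section 10.2 | yes | no | serum |
| Analysis, Section 11.3.4 | yes | no | not stated |

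**The case against.** - **Section 10.1 already requires the C1D1 draw.** This is correct. A reader might infer that the plan has only one pre-treatment sample; the documents do not support that. They contradict each other, and the visit list and schedule table that sites work from are the places that drop the sample.
- **ctDNA and phospho-ERK remain estimable.** This also stands. The ctDNA objective is only partly quantitative, and Section 11.3.4 models repeated samples rather than a single change to C2D1. The tempting conclusion that the plan cannot answer its biomarker objectives goes too far.
- **Sampling during chemotherapy is a corner case.** Exclusion 2 also requires recovery from earlier toxicity to Grade 1 or below at consent (with exceptions for neuropathy and alopecia), a trial-specific draw follows consent, and inclusion 3 requires progression on at least two regimens. These narrow the overlap but do not close it: none sets a gap between the last dose of prior therapy and the screening draw.
- **A C1D1 baseline does not isolate the drug effect.** This is true. Untreated growth would continue from C1D1 to C2D1, and a single arm cannot separate the two. The gain is a shorter and uniform interval. Two pre-treatment draws would also give some view of drift, so the screening sample should stay.
- **Phospho-AKT is covered elsewhere.** It is an exploratory objective in tumour tissue, with a protein array as the tissue assay. To say it is never measured would be wrong. But tissue collection is optional and depends on routine biopsies, so it does not serve the blood endpoint. The title of the assay paper listed in Section 13 refers to sera, so plasma in the objective may be a slip. The Laboratory Manual was not available and may add detail on collection, but Section 11.3.4 would still contain no phospho-AKT analysis.

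**Conclusion.** The point holds as an internal contradiction with a practical consequence, plus a secondary endpoint with no route to a result. A site that follows Section 6.3.1 and Appendix A would have a baseline up to 28 days old, with half of the screening window unprotected by the washout, and up to half of the baseline-to-C2D1 interval spent off study drug. That weakens the ctDNA and phospho-ERK results without making them impossible. Blood phospho-AKT has no described assay or analysis, and plasma and serum must be reconciled.

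The day counts follow from the documents alone. The doubling-time figures rest on an assumption and show the worst case, and the finding does not depend on them. These are secondary endpoints in 7 to 12 evaluable patients. The correction is worth making because it is cheap and the lost samples are irrecoverable, but nothing here touches the primary endpoint, the sample size, the type I error or the power.

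**What to change.** 1. Add a pre-dose C1D1 correlative sample to Section 6.3.1 and to the Appendix A row, matching Section 10.1. Keep the screening sample.
2. In Section 11.3.4, define the C1D1 value as the baseline in the mixed model. For patients already enrolled without one, use the screening value, flagged as such and with its age in days recorded.
3. Either add phospho-AKT to the blood assay in Section 10.2 and to the analysis in Section 11.3.4, or remove it from the blood objectives and endpoints in the synopsis and Sections 3.2 and 3.4.2.
4. Name one matrix for the phosphoproteins, plasma or serum, in the objective, the assay section and the Laboratory Manual.

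**Cost.** Up to 3 × 10 = 30 mL more blood than Section 6.3.1 now schedules, at a visit where safety blood is already drawn, and no more than Section 10.1 already asks for. If phospho-AKT is kept, its assay is added. Section 1.4 reports that three patients had already completed Cycle 1, so baseline timing will be mixed for patients treated before the change, and the report should say so.
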